10.3.3.2 Hepatic function abnormality

Hepatic function abnormality (as defined in Section 10.1.3.) in a study subject, with or without associated clinical manifestations, is required to be reported as "hepatic function abnormal" ***within 24 hours of knowledge of the event*** to The University of Texas MD Anderson Cancer Center and AstraZeneca/MedImmune Patient Safety using the designated Safety e-mailbox (see Section 10.3.2 for contact information), unless a definitive underlying diagnosis for the abnormality (e.g., cholelithiasis or bile duct obstruction) that is unrelated to investigational product has been confirmed.

- If the definitive underlying diagnosis for the abnormality has been established and is unrelated to investigational product, the decision to continue dosing of the study subject will be based on the clinical judgment of the investigator.
- If no definitive underlying diagnosis for the abnormality is established, dosing of the study subject must be interrupted immediately. Follow-up investigations and inquiries must be initiated by the investigational site without delay.

Each reported event of hepatic function abnormality will be followed by the investigator and evaluated by the The University of Texas MD Anderson Cancer Center and AstraZeneca/MedImmune.

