	Grade 2 (AST or ALT > 3 to 5 × ULN and/or TB >1.5 to 3.0 × ULN)	Hold study drug/study regimen dose until Grade 2 resolution to Grade ≤1. 
 • If toxicity worsens, then treat as Grade 3 or Grade 4. • If toxicity improves to Grade ≤1 or baseline, resume study drug/study regimen after completion of steroid taper. 	For Grade 2: 
 – Regular and frequent checking of LFTs (eg, every 1 to 2 days) until elevations of these are improving or resolved. – If no resolution to Grade ≤1 in 1 to 2 days, discuss with [name] and/or [name]. – If event is persistent (>3 to 5 days) or worsens, promptly start prednisone 1 to 2 mg/kg/day PO or IV equivalent. – If still no improvement within 3 to 5 days despite 1 to 2 mg/kg/day of prednisone PO or IV equivalent, consider additional workup and start prompt treatment with IV methylprednisolone 2 to 4 mg/kg/day. – If still no improvement within 3 to 5 days despite 2 to 4 mg/kg/day of IV methylprednisolone, promptly start immunosuppressives (mycophenolate mofetil)^a Discuss with [name] and/or [name] if mycophenolate mofetil is not available. Infliximab should NOT be used.

Specific Immune-mediated Reactions

Adverse Events	Severity Grade of the Event (NCI CTCAE version 4.03)	Dose Modifications	Toxicity Management
			
 Once the patient is improving, gradually taper steroids over ≥ 28 days and consider prophylactic antibiotics, antifungals, and anti-PCP treatment (refer to current NCCN guidelines for treatment of cancer-related infections [Category 2B recommendation]).^a

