	
Grade 3 or 4 (Grade 3: AST or ALT >5 to $20 \times$ ULN and/or TB >3.0 to $10 \times$ ULN)
 
(Grade 4: AST or ALT $>20 \times$ ULN and/or TB $>10 \times$ ULN)
	
For Grade 3:
 
For elevations in transaminases $\leq 8 \times$ ULN, or elevations in bilirubin $\leq 5 \times$ ULN:
 
 Hold study drug/study regimen dose until resolution to Grade ≤ 1 or baseline Resume study drug/study regimen if elevations downgrade to Grade ≤ 1 or baseline within 14 days and after completion of steroid taper. Permanently discontinue study drug/study regimen if the elevations do not downgrade to Grade ≤ 1 or baseline within 14 days 
For elevations in transaminases $>8 \times$ ULN or elevations in bilirubin $>5 \times$ ULN, discontinue study drug/study regimen.
 
Permanently discontinue study drug/study regimen for any case meeting Hy's law criteria (AST and/or ALT $>3 \times$ ULN + bilirubin $>2 \times$ ULN without
	
For Grade 3 or 4:
 
 Promptly initiate empiric IV methylprednisolone at 1 to 4 mg/kg/day or equivalent. If still no improvement within 3 to 5 days despite 1 to 4 mg/kg/day methylprednisolone IV or equivalent, promptly start treatment with immunosuppressive therapy (mycophenolate mofetil). Discuss with [name] and/or [name] if mycophenolate is not available. Infliximab should NOT be used. Perform hepatology consult, abdominal workup, and imaging as appropriate. Once the patient is improving, gradually taper steroids over ≥ 28 days and consider prophylactic antibiotics, antifungals, and anti-PCP treatment (refer to current NCCN guidelines for treatment of cancer-related infections [Category 2B recommendation]).^a

Specific Immune-mediated Reactions

Adverse Events	Severity Grade of the Event (NCI CTCAE version 4.03)	Dose Modifications	Toxicity Management

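### Appendix 1 hepatitis row: some unexplained, non-cholestatic Grade 2 liver values also meet the Hy's-law discontinuation line, and the two Grade 3 lines can both apply to one patient

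*Combined protocol and SAP*

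**What the plan says.** All limits are multiples of ULN, from Appendix 1, Hepatitis (elevated LFTs), unless stated.

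- **Grade 2** is "AST or ALT > 3 to 5" and/or bilirubin above 1.5 to 3.0. Dosing is held. On improvement to Grade 1 or lower, or to baseline, the site is told to "resume study drug/study regimen after completion of steroid taper". The row escalates only if toxicity worsens and does not mention Hy's law.
- **Grade 3** is "Grade 3: AST or ALT >5 to" 20 and/or bilirubin above 3.0 to 10. Under the Grade 3 label there are three lines:
  - Hold line: transaminases up to 8 "ULN, or elevations in bilirubin" up to 5. Here the text is "Resume study drug/study regimen if elevations downgrade to Grade" 1 or lower, or baseline, within 14 days and after the taper.
  - Discontinue line: transaminases above 8 or bilirubin above 5 "ULN, discontinue study drug/study regimen".
  - Hy's-law line: "Permanently discontinue study drug/study regimen for any case meeting" AST and/or ALT above 3 with bilirubin above 2, without initial cholestasis and without an alternative cause.
- The **Grade 4** label follows the Hy's-law line.
- **Section 10.3.3.2** covers AST/ALT above 3 with bilirubin above 2 (defined in Section 10.1.3). If no definitive diagnosis is established, "dosing of the study subject must be interrupted immediately" and follow-up investigations begin.

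**The concern.** A dosing table should give one instruction for one set of laboratory values. Here the Hy's-law thresholds reach down into the Grade 2 range, yet the line stands under Grade 3 and the Grade 2 row carries no exception. A reader who goes to the row matching the patient's grade finds a route back to dosing. A reader who goes on to the next row finds permanent discontinuation. Within Grade 3, the hold and discontinue lines look like complements but are not, because both join their cut-offs with *or*.

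The regimen is two doses four weeks apart (Section 5.2.1). After Cycle 1 Day 1, the next scheduled chemistries are on Cycle 2 Day 1, and results must be reviewed before an infusion (Schedule of Study Assessments). The conflict therefore falls on the decision about dose 2, in patients whose liver pattern Section 10.3.3.2 requires to be reported within 24 hours unless an unrelated diagnosis has been confirmed.

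**Working it through.** No sample size or error rate is involved. The check is whether the table's own regions overlap.

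**Notation.** A is the higher of AST and ALT, and B is total bilirubin, both in × ULN. The table joins the analytes by and/or, so the worse analyte is taken to set the grade.

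- Hold line: A ≤ 8 or B ≤ 5.
- Discontinue line: A > 8 or B > 5.
- Hy's-law numbers: A > 3 and B > 2. The line also needs no initial cholestasis and no alternative cause.

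**Step 1: Grade 2 against Hy's law.** To stay in Grade 2, A ≤ 5 and B ≤ 3. The Hy's-law numbers need A > 3 and B > 2. The intersection is 3 < A ≤ 5 with 2 < B ≤ 3, which is not empty. In that block the conflict arises only when the two clinical conditions are also met.

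**Step 2: the two Grade 3 lines.** The complement of (A ≤ 8 or B ≤ 5) is (A > 8 *and* B > 5). The plan writes *or*, so both lines are true whenever exactly one value is over its cut-off. On the narrow reading, both values must themselves be in the Grade 3 range (5 < A ≤ 20 and 3 < B ≤ 10). The overlap is then:

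- 8 < A ≤ 20 with 3 < B ≤ 5, or
- 5 < A ≤ 8 with 5 < B ≤ 10.

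Every such pair has A > 3 and B > 2. The Hy's-law line can therefore settle the unexplained, non-cholestatic cases. With cholestasis or another cause it does not apply, and nothing chooses between the two lines.

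**Step 3: the wider reading.** If any value above ULN counts as an elevation, the overlap grows to 8 < A ≤ 20 with 1 < B ≤ 5, or 1 < A ≤ 8 with 5 < B ≤ 10. Part of this is outside the Hy's-law numbers altogether: 8 < A ≤ 20 with 1 < B ≤ 2, and 1 < A ≤ 3 with 5 < B ≤ 10.

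**Worked pairs**

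| A, B | Grade | Grade-row instruction | Hy's-law numbers met |
|---|---|---|---|
| 4, 2.5 | 2 | hold, then resume | yes |
| 5, 3 | 2 | hold, then resume | yes |
| 10, 4 | 3 | hold line and discontinue line | yes |
| 7, 6 | 3 | hold line and discontinue line | yes |
| 9, 6 | 3 | discontinue line only | yes |
| 10, 1.8 | 3 | both lines, wider reading only | no |
| 10, 1.0 | 3 | discontinue line only (bilirubin not elevated) | no |

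**Step 4: Section 10.3.3.2.** It requires immediate interruption and work-up and does not say whether dosing may resume. That fits a hold and it fits a later discontinuation. Section 10.1.3 sends management of the abnormality to Appendix 1, so the conflict has to be resolved there.

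**The case against.** The strongest reply is that the Hy's-law line covers *any* case and uses thresholds below the Grade 3 floors (3 against 5, and 2 against 3), so it was meant to override every grade. That is a plausible reading and may well be the intent. The row runs over a page break, so only the order of its lines is relied on here, not indentation. The text still does not state precedence. Nor would the line be idle if confined to Grade 3: at A = 6, B = 4 the hold line applies and the Hy's-law line would change the outcome.

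A second reply is that the Grade 3 cut-offs apply only to an analyte that is itself in the Grade 3 range. On that reading the pair 10 and 1.8 triggers only discontinuation, so that example cannot carry the point. The narrow overlap in Step 2 remains.

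A third reply is that there are other safeguards. Grade 2 resumption needs improvement first; a case not resolved in 1 to 2 days must be discussed; where steroids are used the taper lasts at least 28 days; and the investigator or the company may stop dosing (Section 4.3). These stand, and they make unnoticed re-dosing less likely. They do not remove the conflict: Grade 2 steroids start only if the event persists beyond 3 to 5 days or worsens, so a quickly improving patient may have no taper to complete.

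A reader might also infer that Section 10.3.3.2 gives a third, conflicting instruction. It does not, because interruption is compatible with either outcome.

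**Conclusion.** The inconsistency is real but limited. Appendix 1 gives two outcomes for AST/ALT above 3 to 5 × with bilirubin above 2 to 3 × ULN when there is no initial cholestasis and no alternative cause. It also gives two outcomes in the narrow Grade 3 overlap of Step 2, where the Hy's-law line offers no help if there is cholestasis or another cause. The Grade 3 overlap is wider only if elevations below Grade 3 also count.

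It would go too far to say that the whole numerical Grade 2 block is in conflict, since cholestatic or otherwise explained cases do not meet the Hy's-law line. It would also go too far to say that patients will be re-dosed unnoticed at this single centre. The documents give no rate for these patterns, so no number of affected patients can be put on it; among 15 patients there may be none. No endpoint, stopping boundary or analysis is shown to change. The reason to act is safety: the wording leaves open whether a given patient receives the second of two doses. The result assumes that the worse analyte sets the grade.

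**What to change.** Reconcile the Grade 2 and Grade 3 parts of the hepatitis row:

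- State in the Grade 2 row whether the Hy's-law line takes precedence.
- Reword the Grade 3 hold and discontinue lines so that each combination of AST/ALT and bilirubin leads to one instruction, and say whether an analyte below the Grade 3 range counts as an elevation.
- Optionally, add a cross-reference from Section 10.3.3.2 to Appendix 1.

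Which instruction applies to each combination is for the clinical team to decide. The cost is a wording amendment to one Appendix 1 row. AST, ALT, alkaline phosphatase and total bilirubin are already collected, so no new data are needed.

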Appendix 2. Durvalumab DOSE CALCULATIONS

For durvalumab dosing done depending on subject weight:

1. Cohort dose: X mg/kg
2. Subject weight: Y kg
3. Dose for subject: $XY \text{ mg} = X \text{ (mg/kg)} \times Y \text{ (kg)}$
4. Dose to be added into infusion bag:

$$\text{Dose (mL)} = XY \text{ mg} / 50 \text{ (mg/mL)}$$

where 50 mg/mL is durvalumab nominal concentration.

The corresponding volume of durvalumab should be rounded to the nearest tenth mL (0.1 mL). Dose adjustments for each cycle are only needed for greater than 10% change in weight.

5. The theoretical number of vials required for dose preparation is the next greatest whole number of vials from the following formula:

$$\text{Number of vials} = \text{Dose (mL)} / 10.0 \text{ (mL/vial)}$$

Example:

1. Cohort dose: 10 mg/kg
2. Subject weight: 30 kg
3. Dose for subject: $300 \text{ mg} = 10 \text{ (mg/kg)} \times 30 \text{ (kg)}$
4. Dose to be added into infusion bag:

$$\text{Dose (mL)} = 300 \text{ mg} / 50 \text{ (mg/mL)} = 6.0 \text{ mL}$$

5. The theoretical number of vials required for dose preparation:

$$\text{Number of vials} = 6.0 \text{ (mL)} / 10.0 \text{ (mL/vial)} = 1 \text{ vials}$$

Appendix 3. Durvalumab DOSE VOLUME CALCULATIONS

For durvalumab flat dosing:

1. Cohort dose: X g

2. Dose to be added into infusion bag:

$$\text{Dose (mL)} = X \text{ g} \times 1000 / 50 \text{ (mg/mL)}$$

where 50 mg/mL is durvalumab nominal concentration.

The corresponding volume of durvalumab should be rounded to the nearest tenth mL (0.1 mL).

3. The theoretical number of vials required for dose preparation is the next greatest whole number of vials from the following formula:

$$\text{Number of vials} = \text{Dose (mL)} / 10.0 \text{ (mL/vial)}$$

Example:

1. Cohort dose: 1.5 g

2. Dose to be added into infusion bag:

$$\text{Dose (mL)} = 1.5 \text{ g} \times 1000 / 50 \text{ (mg/mL)} = 30.0 \text{ mL}$$

3. The theoretical number of vials required for dose preparation:

$$\text{Number of vials} = 30.0 \text{ (mL)} / 10.0 \text{ (mL/vial)} = 3 \text{ vials}$$

Appendix 4. Tremelimumab DOSE CALCULATIONS

For tremelimumab dosing done depending on subject weight:

1. Cohort dose: X mg/kg
2. Subject weight: Y kg
3. Dose for subject: $XY \text{ mg} = X \text{ (mg/kg)} \times Y \text{ (kg)}$
4. Dose to be added into infusion bag:

$$\text{Dose (mL)} = XY \text{ mg} / 20 \text{ (mg/mL)}$$

where 20 mg/mL is tremelimumab nominal concentration.

The corresponding volume of tremelimumab should be rounded to the nearest tenth mL (0.1 mL). Dose adjustments for each cycle are only needed for greater than 10% change in weight.

5. The theoretical number of vials required for dose preparation is the next greatest whole number of vials from the following formula:

$$\text{Number of vials} = \text{Dose (mL)} / 20.0 \text{ (mL/vial)}$$

Example:

1. Cohort dose: 1 mg/kg
2. Subject weight: 30 kg
3. Dose for subject: $30 \text{ mg} = 1 \text{ (mg/kg)} \times 30 \text{ (kg)}$
4. Dose to be added into infusion bag:

$$\text{Dose (mL)} = 30 \text{ mg} / 20 \text{ (mg/mL)} = 1.5 \text{ mL}$$

5. The theoretical number of vials required for dose preparation:

$$\text{Number of vials} = 1.5 \text{ (mL)} / 20.0 \text{ (mL/vial)} = 1 \text{ vials}$$

Appendix 5. Tremelimumab DOSE VOLUME CALCULATIONS

For tremelimumab flat dosing:

1. Cohort dose: X mg
2. Dose to be added into infusion bag:

$$\text{Dose (mL)} = X \text{ mg} / 20 \text{ (mg/mL)}$$

where 20 mg/mL is tremelimumab nominal concentration

The corresponding volume of tremelimumab should be rounded to the nearest tenth mL (0.1 mL).

3. The theoretical number of vials required for dose preparation is the next greatest whole number of vials from the following formula:

$$\text{Number of vials} = \text{Dose (mL)} / 20 \text{ (mL/vial)}$$

Example:

1. Cohort dose: 75 mg
2. Dose to be added into infusion bag:

$$\text{Dose (mL)} = 75 \text{ mg} / 20 \text{ (mg/mL)} = 3.8 \text{ mL}$$

3. The theoretical number of vials required for dose preparation:

$$\text{Number of vials} = 3.8 \text{ (mL)} / 20 \text{ (mL/vial)} = 1 \text{ vial}$$
